6.3.1. Intent-to-Treat Population

The ITT population includes all randomized subjects regardless of whether they received the study treatment or not. This analysis population will be used for the analysis of clinical cure.

6.3.2. Microbiological Intent-to-Treat Population

The micro-ITT population includes all randomized subjects who have a positive baseline bacterial culture of urine. Positive baseline culture is defined as a culture grown from a urine sample collected prior to treatment with study drug that has $\geq 10^5$ colony forming units (CFU)/mL (50,000 and above is an allowed cut-off provided it is a causative uropathogen) for non-catheter specimens OR $\geq 10^4$ CFU/mL for catheter specimens of a single species of bacteria that causes cUTI. Subjects will not be excluded from this population based on events that occur after randomization. Whether the organism is a causative pathogen is collected in the data system as MIB.MIBP1UTI, MIB.MIBP2UTI, etc. A urine culture will be defined as contaminated if three organisms are detected or contaminants are indicated; when there isn't at least one non-contaminant pathogen with $\geq 50,000$ CFU/mL and all contaminant pathogens are $\leq 40,000$ CFU/mL. Multiple imputation as described in Section 8.4.1 will be used in the case of missing values for treatment success, clinical cure, or microbiological success at TOC and EOT in the micro-ITT population.

6.3.3. Complete Case Populations

The CC-TOC and CC-EOT populations include all subjects from the micro-ITT population who received at least one dose of study product and have non-missing values for treatment success at TOC or EOT, respectively. Exclusion from CC analysis population due to a urine culture that was contaminated at TOC or EOT will be reviewed prior to finalization. Subjects in the CC analysis populations are analyzed as randomized without imputation. Both CC populations will be used for analysis of exploratory endpoints.

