### 5.3.5. Subject Replacement

Subjects/subject's LAR who sign the ICF and are randomized but do not receive study drug (e.g decline assignment to a specific strategy), or are randomized and treated, but subsequently withdraw; or are withdrawn or terminated from the trial; or are lost to follow-up will not be replaced. If the study drop-out rate exceeds 20%, the Principal Investigator (PI) will, in consultation with the ARLG and the sponsor, determine if replacement rules and/or study design need to be revised.

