5. SAMPLE SIZE CONSIDERATIONS

This is a Phase IV multicenter, open-label, randomized pragmatic superiority clinical trial comparing two strategies for step-down oral therapy for cUTI. The basic null hypothesis of this trial is:

H0: The probability of success (clinical cure and microbiological cure) at TOC is not conditional on the treatment strategy.

This hypothesis testing question will result in one of three statements regarding the results of this trial:

1. Strategy 1 is superior to Strategy 2.
2. Strategy 2 is superior to Strategy 1.
3. Evidence from the trial is insufficient to conclude that either strategy is superior.

The primary analysis will use the micro-ITT population, defined as all randomized subjects who have a positive baseline bacterial culture of urine. Subjects will not be excluded from this population based upon events that occurred post-randomization (e.g., loss to follow-up). An assumption of 92% micro-ITT eligibility is made for the sample size calculations. If 634 subjects are enrolled with 1:1 allocation, 291 subjects per arm would be expected to qualify for the micro-ITT population. Assuming a 10% difference in treatment success at TOC, with 80% success for one strategy and 70% success for the other strategy, there will be 80% power to reject the null hypothesis using a two sided ztest (without continuity correction), with a Type I error rate of 5%. These calculations assume an interim analysis after 40% of subjects have completed the study, with Type I error controlled using Lan DeMets with an O'Brien Fleming spending function. The specific success rates of 70% and 80% are based on a 10% clinically significant difference an approximate rate of success consistent with example calculations in the FDA guidance for cUTI studies. Sample size calculations were computed using PASS 2008 software. The calculations do not adjust for dropout, because analysis methods will include subjects that have dropped out early, assuming they meet micro-ITT criteria (Section 6.3.1).

If true success rates are instead 65% and 75%, there will be 75% power to conclude a difference in the strategies. If true success rates are 80% and 90%, there will be 92% power to conclude a difference.

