6.3. Analysis Populations

The primary analysis will be performed using the micro-ITT population. Other analyses, as specified below, may use the complete cases (CC) at Test of Cure or End of Therapy (CC-TOC or CC-EOT) populations. Analyses of the micro-ITT population will include imputation for missing data (Section 8.4), while analyses of the CC populations will not contain missing data by design. Analysis of clinical cure will use the ITT analysis population and will include imputation for missing data. Analysis of clinical cure will be repeated to use all subjects in ITT with complete data. Analysis of unsolicited events will use the Fosfomycin safety analysis population while analysis of solicited events will use both the Safety and Fosfomycin Safety populations.

Reasons for exclusion from each analysis population are summarized in [Table 7](#) and shown by subject in [Listing 4](#). Excluded subjects might satisfy multiple criteria justifying their exclusion but will have only the first exclusion criteria met for a given population indicated in [Table 7](#) and [Listing 4](#). The reason indicated will be determined by the following rules in order.

ITT Analysis Exclusion Reasons:

- Subject not randomized

Micro-ITT Analysis Exclusion Reasons:

- Subject does not have a baseline culture from a urine sample taken prior to treatment with study drug
- Baseline culture is not positive for a uropathogen or is contaminated

CC-TOC Analysis Exclusion Reasons:

- Subject not in micro-ITT population
- Subject not treated with at least one dose of study product
- Early termination before TOC
- Missing urine culture or had a urine culture that was contaminated at TOC

CC-EOT Analysis Exclusion Reasons:

- Subject not in micro-ITT population

-
- Subject not treated with at least one dose of study product
 - Early termination before EOT
 - Missing urine culture or had a urine culture that was contaminated at EOT

Safety Analysis Exclusion Reasons:

- Subject not treated with at least one dose of study product

Fosfomycin Safety Analysis Exclusion Reasons:

- Subject not treated with at least two doses of Fosfomycin

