- Indicator of subject enrolled at the site with the third most number of subjects enrolled (binary indicator)
- Indicator of subject enrolled at the site with the fourth most number of subjects enrolled (binary indicator)
- Indicator of subject enrolled at the site with the least number of subjects enrolled (binary indicator)
 - Note: the site with the most number of subjects enrolled is reference for site. Language is written to allow for an arbitrary number of sites. In the event of a number of ties for the number of subjects enrolled, tied sites will be ordered in ascending alphanumeric order in the list of model variables.
- Age at enrollment
- Sex (Male is the reference)
- Indicator for pyelonephritis (No is the reference)
- Number of species detected in the urine at baseline (1 is the reference)

The actual list of MI model variables for each subject-specific imputation model will follow the ordering above but omit variables with missing values. The below pseudo-code / SAS code outlines the creation of 20 multiple imputation datasets. Note that the seeds used in the actual analysis must follow the specification given in the pseudo-code and subjects must be processed in the order described in the pseudo-code. Clinical cure and microbiological success will simultaneously be imputed with composite cure at each respective time point. The pseudo-code is in terms of TOC endpoints, but the general logic is also applicable to the EOT.

*Outcome variables: trtsuccess clincure microsuccess

DEFINE i=index variable for subjects having treatment success imputed.

Subjects requiring imputation are sorted in ascending order
by PATID.

DEFINE N=number of subjects requiring imputation

DEFINE g&i=analysis dataset containing predictors and treatment success for
CC-TOC subjects as well as subject i (only one subject not in
CC-TOC included). Note that CC-TOC subjects that are missing a value
for one or more variables in the subject-specific imputation model are excluded.

DEFINE imp_g&i = g&i, with 20 imputed values for the missing treatment success
added by PROC MI

DEFINE &&modelVars_&i = list of observed variables in subject i (site1, site2, site3, site4, age, sex,
treatment strategy, pyelonephritis, Nbacterias), to be used for imputation of treatment success, clinical cure,
and microbiological cure.

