Step 1: Imputation model: This model will generate 20 datasets with each dataset containing original complete data along with imputed values for subjects with missing endpoint.

```
%do i=1 %to &N;
```

```
PROC MI data= g&i out= imp_g&i seed= 22131&i NIMPUTE=20 noprint;
  Var &&modelVars_&i trtsuccess_TOC clincure_TOC microsuccess_TOC;
  monotone regression(trtsuccess_TOC = &&modelVars_&i);
  monotone regression(clincure_TOC = &&modelVars_&i);
  monotone regression(microsuccess_TOC = &&modelVars_&i);
```

```
run;
```

```
%end;
```

imp_g&i will be subset to contain only rows for the subjects with imputed treatment success, clinical cure,
and microbiological success and merged together and with CC-TOC data to create the twenty complete
multiply imputed datasets

Step 2: Analysis model: This model will fit regression models to the 20 complete datasets to obtain parameter estimates for treatment success, clinical cure, microbiological success.

```
proc reg data= imp_g outest= out_trts covout noprint;
```

```
model trtsuccess= trt /clb alpha=0.05;
```

```
by _imputation_;
```

```
run;
```

```
proc reg data= impdata outest= out_clinc covout noprint;
model clincure= trt /clb alpha=0.05;
by _imputation_;
run;

proc reg data= impdata outest= out_micros covout noprint;
model microsucceed= trt/clb alpha=0.05;
by _imputation_;
run;
```

Step 3: Combine estimates from models in step 2 to obtain overall estimates summarized over 20 imputed datasets;

```
proc mianalyze data= out_trts alpha = 0.05;
modeleffects trt;
ods output ParameterEstimates=parms_trts;
run;

proc mianalyze data= out_clinc alpha = 0.05;
modeleffects trt;
ods output ParameterEstimates=parms_clinc;
run;

proc mianalyze data= out_micros alpha = 0.05;
modeleffects trt;
ods output ParameterEstimates=parms_micros;
run;
```

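### Read literally, the one-dose condition in the complete-case definition drops untreated subjects with known outcomes from the primary micro-ITT datasets

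*SAP*

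**What the plan says.** **Complete-case sets.** SAP 6.3.3 states that CC-TOC and CC-EOT "include all subjects from the micro-ITT population who received at least one dose of study product and have non-missing values for treatment success" at the relevant visit. Dosing and a known outcome are two separate conditions. SAP 6.3 and mock Table 7 confirm this: "Subject not treated with at least one dose of study product" is its own exclusion reason, ranked ahead of early termination and of a missing or contaminated culture.

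**Primary datasets.** The pseudo-code in SAP 8.4.1 loops over a restricted list: "DEFINE i=index variable for subjects having treatment success imputed". Each imputation model is fitted to the CC-TOC subjects together with the one subject being imputed. Only the imputed rows are kept, and these are "merged together and with CC-TOC data to create the twenty complete" datasets used for the primary test. The same logic applies at EOT.

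**Population rule.** SAP 6.3.2 says of micro-ITT: "Subjects will not be excluded from this population based on events that occur after randomization". SAP 5 repeats it: "Subjects will not be excluded from this population based upon events that occurred post-randomization". SAP 6.3.2 also limits multiple imputation, which "will be used in the case of missing values for treatment success, clinical cure, or microbiological success at TOC and EOT in the micro-ITT population".

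**Competing definition.** SAP 8.2.2 describes CC-TOC as micro-ITT subjects with no missing treatment success, and the Table 26 note likewise has no dose condition.

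**Untreated subjects are foreseen.** Protocol 5.3.5 refers to subjects who are "randomized but do not receive study drug (e.g decline assignment to a specific strategy") and says they are not replaced. SAP 3.3 defines Day 1 for subjects who received no study product, and mock Table 9 has a zero-dose column.

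**The concern.** An untreated subject can have a known outcome. Under SAP 3.3, parenteral antibiotic therapy at any time after randomisation fails clinical cure and therefore fails treatment success. If such a subject is left out of the assembled datasets, the analysis labelled micro-ITT is no longer the full micro-ITT set.

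The trial is open-label (Protocol 5.3.2), so refusal of study drug can follow knowledge of the allocation and can differ between arms. That is the kind of exclusion an intention-to-treat rule is meant to prevent.

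Two further effects follow from the same condition. The regression used to impute missing outcomes is fitted to treated subjects only. The complete-case sensitivity analysis applies the same exclusion, so it cannot reveal the problem. Protocol 11.4 describes that sensitivity analysis without a dose condition, and SAP 12 does not list the condition as a change.

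**Working it through.** **Plan's own figures.** SAP 5 gives 12% power for 48 micro-ITT subjects at 80% vs 70%, two-sided 5%, no continuity correction. With 24 per arm (an even split is an assumption):
- null SE = √(2 × 0.75 × 0.25 / 24) = 0.1250
- alternative SE = √((0.80 × 0.20 + 0.70 × 0.30) / 24) = 0.1242
- power = Φ((0.10 − 1.96 × 0.1250) / 0.1242) = Φ(−1.17) ≈ 12.1%

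The planned 80% with 291 per arm also reproduces: 79.7% for a fixed design, and 79.4–80.0% with the O'Brien-Fleming look at 40%. None of these figures turns on the present point, which concerns which rows enter the dataset.

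**Row logic for micro-ITT subjects at TOC.**

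| Subject | In CC-TOC (6.3, 6.3.3)? | In imputation loop (8.4.1)? | In primary dataset? |
|---|---|---|---|
| Treated, outcome observed, no other 6.3 exclusion | yes | no | yes |
| Treated, outcome missing | no | yes | yes, imputed |
| Untreated, outcome missing | no | yes | yes, imputed from a model fitted to treated subjects |
| Untreated, outcome observed | no (no dose) | no (nothing missing) | **no** |

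Under the dose-free definition in 8.2.2, the last row enters CC-TOC and is retained. The two definitions can therefore give different primary results from the same data.

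**Size.** Let k of the 24 subjects in one arm be untreated known failures, and let s be the success rate among the other 24 − k.
- Rate with failures kept: s(24 − k)/24
- Rate with failures omitted: s
- Shift: s × k/24

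| k | s = 0.75 | s = 0.80 |
|---|---|---|
| 0 | 0 | 0 |
| 1 | 3.1 points | 3.3 points |
| 2 | 6.3 points | 6.7 points |
| 3 | 9.4 points | 10.0 points |

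With 80% success among treated subjects in both arms and k failures in Strategy 1, keeping them gives a difference of −3.3, −6.7 and −10.0 points for k = 1, 2, 3. Omitting them gives 0. A simulation of 3,000 trials agreed within sampling error: −3.5, −7.0 and −9.8 with failures kept, and −0.2, −0.4 and +0.2 with failures omitted.

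**The case against.** The strongest reply is that the governing text is already right. SAP 6.3.2 bars post-randomisation exclusions and reserves imputation for missing values. Table 20 defines N as the number in the micro-ITT population, so a dropped row would not reconcile with it. SAP 8.2.2 and the Table 26 note omit the dose condition, and 8.4.1 is labelled pseudo-code. A careful programmer might well keep the untreated subject. This stands as far as it goes: it shows that the SAP is inconsistent, not that it is clear.

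The affected group may also be empty. First dosing is due on the calendar day of randomisation (Protocol, Visit 01) and is directly observed (Protocol 6.4). Protocol 5.3.5 gives no expected count of decliners. This stands too, and limits the size.

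Three stronger readings are tempting, and the documents do not support them:
- *Observed outcomes are replaced by values from treated subjects.* The loop covers only subjects whose outcome is being imputed, and PROC MI fills only missing values. Replacement would require someone to blank the observed value first. No donor values are copied: imputations are draws from one linear regression fitted across both arms, with strategy as a covariate.
- *An untreated subject with a missing outcome is mishandled because the outcome is imputed.* That is the planned missing-at-random handling. Changing the dose wording would not recover an unseen failure.
- *Anyone who declines is a failure who gets credited with roughly the arm's success rate.* No section says what decliners receive, so failure cannot be presumed. A known failure would be omitted, not given a rate.

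Finally, with 24 per arm at 80% vs 70%, the 95% interval half-width is about 24 points (1.96 × 0.1242), and SAP 5 already advises against superiority conclusions. That tempers the practical consequence. It does not justify leaving the primary dataset undetermined.

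**Conclusion.** The point holds as a conflict in the SAP's wording. Taken literally, 6.3 and 6.3.3 combined with 8.4.1 omit an untreated micro-ITT subject with an observed outcome, against 6.3.2. Under 8.2.2 and the Table 26 note the same subject is kept. A reader might infer that the primary analysis has become a treated-subjects analysis; that goes too far, because untreated subjects with missing outcomes remain in it and the SAP also supports the inclusive reading.

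The shift is about 3 points in one arm per omitted known failure. This assumes an even 24/24 split, 75–80% success among the arm's other subjects, and that the omitted subject is a failure. Two in the same arm would shift the difference by 6 to 7 points, against a design difference of 10. The documents do not say how many such subjects exist; if there are none, there is no effect.

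**What to change.** 1. In SAP 8.4.1, build the imputed datasets from all micro-ITT subjects. Carry forward every observed outcome regardless of dosing, fit the imputation model on all micro-ITT subjects with observed outcomes, and impute only missing values. Apply the same rule at EOT, and to clinical cure and microbiological success.
2. Use one complete-case definition throughout. Either remove the dose condition from 6.3, 6.3.3 and Table 7, in line with 8.2.2 and the Table 26 note, or keep it only for a separately named treated complete-case set that does not feed 8.4.1.
3. Score untreated subjects by the SAP 3.3 definitions wherever their data allow.

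The first step alone repairs the primary analysis; the second removes the inconsistency and restores the sensitivity analysis described in Protocol 11.4. The cost is SAP wording and a matching change to the program. No new data are needed.

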6.3.4. Safety Population

The Safety Population includes all enrolled subjects who received at least one dose of study drug. The analyses on the Safety Population will be performed using the actual treatment received.

6.3.5. Fosfomycin Safety Population

The Fosfomycin Safety Population includes all enrolled subjects who received at least two doses of Fosfomycin.

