## 11.4. Final Analysis Plan

Planned analyses of all primary and secondary endpoints will be described in detail in the SAP to be prepared by the DCC and finalized prior to unblinding of the study data.

The primary analysis will be a superiority analysis of treatment success at TOC by study arm in the micro-ITT analysis population. Multiple imputation will be used in the case of missing values for treatment success at TOC in the micro-ITT population. The test of the null hypothesis of no difference between the strategies for the primary outcome (Section 11.1) will be performed using linear regression, and will include site, pyelonephritis, and number of bacterial species detected in the urine at baseline as covariates. Further details of the analysis, including the multiple imputation model, will be described thoroughly in the SAP. As a secondary analysis, a difference in treatment success at EOT by treatment strategy will be tested in the micro-ITT population, using methods analogous to the primary analysis. Sensitivity analyses will be performed for the primary analysis including a complete case analysis in which subjects are analyzed as randomized without imputation and tipping point analyses.

The safety analysis population will include all subjects receiving at least one dose of study drug. 95% confidence intervals of frequencies of solicited and unsolicited adverse events, SAEs and AESIs will be provided using the Wilson score method.

Frequency and number of solicited adverse events of grade 2 and above will be reported by treatment arm, study day, and severity, and differences between treatment arms in frequency of grade 2 and above severity solicited adverse events after the first dose of study drug will be tested using Fisher Exact Tests. For subjects receiving fosfomycin, frequency and number of each solicited adverse event of grade 2 and above severity occurring any time from date of first dose of fosfomycin in subjects receiving 2 or more doses until 2 days after last dose of fosfomycin will be tabulated.

Frequency and number of SAEs in subjects receiving at least two doses of fosfomycin during the trial will be tabulated.

For subjects receiving fosfomycin, frequency of each unsolicited adverse event of grade 2 and above severity occurring in subjects receiving at least two doses of fosfomycin until 2 days after last dose of fosfomycin will be tabulated overall and by MedDRA® System Organ Class and Preferred Term.

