3.2.2. Secondary Endpoints

1. The number of solicited and unsolicited adverse events (AEs) grade 2 and above in subjects receiving fosfomycin for the duration of fosfomycin use until 2 days after last dose.
2. The number of serious adverse events (SAEs) in subjects receiving at least two doses of fosfomycin during the trial.
3. The difference in rates and severity of solicited AEs in subjects in Strategy 1 and Strategy 2.
4. The difference in the proportion of subjects achieving treatment success at EOT between Strategy 1 and Strategy 2.

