9.3. Adverse Events

All summaries of solicited AEs will be presented for the Safety Population and repeated for the Fosfomycin Safety Population. Summaries of unsolicited AEs will only be provided for the Fosfomycin Safety Population.

When calculating the incidence of AEs over multiple days (i.e., on a per subject basis), each subject will only be counted once and any repetitions of AEs within a subject will be ignored; the denominator will be the total population size on the first day of the time period (Day 1). For tabulation of AEs by day, the denominator will be the number of subjects enrolled and not withdrawn from the study by the day being described. All AEs reported will be included in the summaries and analyses.

A summary of all AEs will be provided in Table 34 for the Fosfomycin safety population. A summary of all AEs that occurred in $\geq 5\%$ of subjects in the Fosfomycin safety population in any treatment group will be provided in Table 35. A summary of any grade 2 and above solicited AE, any AE that led to discontinuation of the study product, and any AESI will be provided in Table 36. Among subjects who took at least two doses of fosfomycin, the frequency and percentage of subjects who experienced at least one solicited AE, unsolicited AE, and SAE, and subjects who discontinued fosfomycin in any treatment strategy will be summarized in Table 37.

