9.3.1. Solicited Events and Symptoms

Solicited AEs are AEs that are common following administration of these types of antibiotics. The solicited AEs will be collected after first dose of study product is given and until the EOT. If a subject is on fosfomycin, solicited AEs will be collected for 2 days after last dose of fosfomycin or until EOT, whichever occurs later.

Solicited events were recorded for trial Days 1-12, or until study completion or termination, as the maximum severity for each day. Only grade 2 and above solicited AEs will be reported. Target solicited events include insomnia, headache, dizziness, nausea, vomiting, constipation, diarrhea, back pain, rhinitis, pharyngitis, allergic reaction, candidiasis. The solicited events were measured by grading scales as defined in Table 3.

When calculating the incidence of solicited events, each subject will be counted once at the highest severity per day, and any repetitions will be ignored. For summaries presented separately for each treatment group, the denominator will be the number of subjects who received at least one dose of the treatment with non-missing data for the event summarized.

The number and percentage of subjects reporting at least one solicited adverse event of moderate severity or higher will be summarized for each solicited symptom and any symptom in Table 38 for the Safety analysis population. For each event, the denominator is the number of subjects in the applicable treatment group who received at least one dose of study product with non-missing data for the specific event. The 95% CIs calculated using Wilson methodology from a binomial distribution (SAS Proc Freq with a binomial option) will be presented. This analysis will be repeated in Table 39 to include subjects in the Fosfomycin safety analysis population who are those who received at least two doses of Fosfomycin.

For each systemic and any systemic event, the maximum severity over 12 days after the first dose will be summarized. The number and percentage of subjects reporting each event will be summarized by the maximum severity and treatment group. For each event, the denominator is the number of subjects who received the applicable treatment with non-missing data for the specific event. The 95% CI calculated using

Wilson methodology from a binomial distribution (SAS Proc Freq with a binomial option) will be presented [Table 40](#) for the Safety population and [Table 41](#) for the Fosfomycin safety population.

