Notes: N = Number of subjects in the Safety Population. Subjects are counted once for each category, regardless of the number of events.
AESI = Adverse Event of Special Interest.

Table 37: Number and Percentage of Adverse Events – Fosfomycin Safety Population*

[Implementation note: This table will be generated for the CSR and will be included in the paper manuscript as Table 5.]

| Adverse Event | All Subjects (N = X) | |
|---|-------------------------|---|
| | n | % |
| Any solicited adverse event grade 2 and above | x | x |
| Any unsolicited adverse event grade 2 and above | x | x |
| Any serious adverse event | x | x |
| Discontinuation of Fosfomycin in any strategy | x | x |

Notes: N = Number of Subjects who received 2 or more doses of Fosfomycin in any treatment group. Subjects are counted once for each category, regardless of the number of events.

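### The fosfomycin-specific safety tables require two doses, so subjects who stop fosfomycin after one dose are missing from their solicited-event and discontinuation rates, in conflict with secondary endpoint 1

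*SAP*

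**What the plan says.** The SAP defines two exposure-based safety sets. In 6.3.4, "The Safety Population includes all enrolled subjects who received at least one dose of study drug". In 6.3.5, "The Fosfomycin Safety Population includes all enrolled subjects who received at least two doses of Fosfomycin".

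The secondary endpoints in SAP 3.2.2 (and Protocol 3.2.2) treat exposure differently from one line to the next. Endpoint 1 is "The number of solicited and unsolicited adverse events (AEs) grade 2 and above in subjects receiving fosfomycin for the duration of fosfomycin use", continuing to 2 days after the last dose, with no minimum number of doses. Endpoint 2 is "The number of serious adverse events (SAEs) in subjects receiving at least two doses of fosfomycin during the trial", with the minimum written in.

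The analysis text adds a minimum that endpoint 1 lacks. Protocol 11.4 has fosfomycin solicited events counted "from date of first dose of fosfomycin in subjects receiving 2 or more doses until 2 days after last dose of fosfomycin will be tabulated", and SAP 4.5 repeats this.

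On presentation, SAP 9.3 says: "All summaries of solicited AEs will be presented for the Safety Population and repeated for the Fosfomycin Safety Population". On collection, SAP 9.3.1 says: "The solicited AEs will be collected after first dose of study product is given and until the EOT". Unsolicited AEs (Protocol 9.2.3) and SAEs (Protocol 9.2.4) are recorded only in subjects with at least two fosfomycin doses.

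Table 37 in SAP Appendix 1, intended for the manuscript, pools the two-dose set across strategies and includes the row "Discontinuation of Fosfomycin in any strategy".

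**The concern.** Membership of the fosfomycin set depends on having gone on to a second dose. A subject who cannot tolerate the first dose and stops is one whom a tolerability summary should show, yet that subject leaves both numerator and denominator.

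The collection rules explain the two-dose condition for unsolicited AEs and SAEs, because nothing was recorded below two doses. They do not explain it for solicited events, which are recorded from the first dose, or for discontinuation, which is recorded for every subject. Assessing the safety of fosfomycin is the first secondary objective, and Table 37 is its pooled summary.

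**Working it through.** The documents give no count of subjects who stopped after one dose, so there is no plan figure to reproduce. The check is a mapping of tables to populations, followed by an illustration of scale.

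**Mapping (SAP 9.3, 9.3.1 and Appendix 1)**

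| Content | Safety Population, at least 1 dose | Fosfomycin Safety Population, at least 2 doses |
|---|---|---|
| Overall summaries | 36 | 34, 35, 37 |
| Solicited events by symptom | 38 | 39 |
| Solicited events by day | 40 | 41 |
| By day and severity | 42 | 43 |
| Maximum severity | 44 | 45 |
| Discontinuation | 36: AE-driven only; fosfomycin in Strategy 1, levofloxacin in Strategy 2 | 37: fosfomycin in either strategy, no reason specified |

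Two cases follow.

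- *Strategy 1, stops after one fosfomycin dose because of an AE.* Absent from the right-hand column, present in the left-hand one.
- *Strategy 2, switched to fosfomycin, stops it after one dose.* Solicited events appear in the Safety Population tables, in the Strategy 2 column. The stopping of fosfomycin is counted nowhere: Table 36 looks only at levofloxacin in that arm, and Table 37 needs two doses.

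**Direction for the Table 37 discontinuation row.** Let n be all subjects with at least one fosfomycin dose, k those who stop after the first, and a those who stop later. This takes k to be subjects who stopped early, not subjects whose course was a single dose.

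- Two-dose rate: a/(n − k)
- One-dose rate: (a + k)/n
- Difference: (a + k)/n − a/(n − k) = k(n − a − k)/[n(n − k)]

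Since a ≤ n − k, the difference is never negative. The row is understated or unchanged.

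**Scale.** Assumptions: n = 62/2 = 31 (62 enrolled, 1:1, all dosed as assigned, switches from Strategy 2 ignored); a = 2 or 4 and k = 1 to 3 are invented for illustration.

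| a | k | Two-dose rate | One-dose rate | Difference (points) |
|---|---|---|---|---|
| 2 | 1 | 2/30 = 6.7% | 3/31 = 9.7% | 3.0 |
| 2 | 2 | 2/29 = 6.9% | 4/31 = 12.9% | 6.0 |
| 2 | 3 | 2/28 = 7.1% | 5/31 = 16.1% | 9.0 |
| 4 | 1 | 4/30 = 13.3% | 5/31 = 16.1% | 2.8 |
| 4 | 2 | 4/29 = 13.8% | 6/31 = 19.4% | 5.6 |
| 4 | 3 | 4/28 = 14.3% | 7/31 = 22.6% | 8.3 |

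With k = 0 the two rates are equal. For a = 2 and k = 2 the Wilson 95% intervals are 1.9 to 22.0% (two-dose) and 5.1 to 28.9% (one-dose). They overlap widely, as expected at this sample size.

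**Direction for solicited events.** Suppose 8 of the subjects who continue have a grade 2 or higher event and k = 2. The two-dose table shows 8/29 = 27.6%. If both first-dose stoppers had an event, the one-dose rate is 10/31 = 32.3%; if neither did, it is 8/31 = 25.8%. The two-dose table can therefore err either way.

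**The case against.** A reader might infer that first-dose stoppers disappear from the trial's solicited-event and discontinuation rates altogether. The documents do not support that. Every solicited-event summary is given first for the one-dose Safety Population, and Table 36 reports AE-driven stopping of fosfomycin in Strategy 1 on the same basis. Table 36 also matches exploratory endpoint 14, which compares stopping of the initial drug between strategies.

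A reader might also infer that the SAP departed from the protocol. It did not: Protocol 11.4 carries the two-dose wording for fosfomycin solicited events.

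Third, a uniformly downward bias is tempting but not established. Subjects may stop after one dose for reasons other than intolerance, such as withdrawal of consent or a baseline blood culture that turns positive after randomization. Removing event-free subjects raises the solicited-event rate.

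Fourth, there is a design reason. Endpoint 1 combines solicited with unsolicited events, and the latter exist only from the second dose, so a single denominator keeps Tables 34 and 37 coherent. Finally, Tables 6 and 9 and Listings 1 and 7 show doses received and reasons for stopping or adjustment, so much of the missing information can be reconstructed.

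All of this narrows the point without removing it. The Safety Population table shells have strategy columns, and both strategies allow a switch of drug, so they do not isolate fosfomycin recipients across arms as the fosfomycin safety objective requires. Protocol 11.4 sets no two-dose condition for discontinuation, so prespecification does not cover that row of Table 37. Coherence of denominators is a reason to footnote two of them, not to leave out data already collected. Listings let a determined reader recover the subjects, but the manuscript table would still show the selected rate.

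**Conclusion.** The point holds for the fosfomycin-specific tables. Their two-dose condition conflicts with the wording of secondary endpoint 1, and the conflict is between endpoint and analysis text inside both documents. It leaves one real hole: the Strategy 2 subject switched to fosfomycin who stops after a single dose.

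The direction is certain only for the discontinuation row of Table 37. For solicited events it depends on whether the one-dose stoppers had grade 2 or higher events. The size cannot be determined from the documents. It is zero if nobody stopped after dose 1; otherwise it is roughly 3 points per subject for the discontinuation row if about 31 were exposed, and somewhat less per subject if switches from Strategy 2 enlarge that number. Neither the primary efficacy analysis nor the by-strategy safety comparison is affected. The change should be made before the final tables are produced.

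**What to change.** 1. For solicited events in the fosfomycin-specific tables (39, 41, 43, 45 and the solicited content of 34, 35 and 37) and for the fosfomycin discontinuation row of Table 37, use all subjects with at least one fosfomycin dose in either strategy.
2. Record this in SAP Section 12 as a change from Protocol 11.4, and revise SAP 4.5 and 6.3.5 to match.
3. Keep the two-dose set for unsolicited AEs and SAEs. Events after a single dose were not collected and no change of population can recover them.
4. Show the separate denominators in Tables 34 and 37, with a footnote giving the number who stopped after one fosfomycin dose, by strategy, and why.

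If the two-dose set is kept throughout, the minimum is to state the condition in endpoint 1 and disclose the exclusion beside Table 37.

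The cost is SAP wording, a second denominator within some tables and a documented departure from Protocol 11.4. No new data are needed. The fosfomycin figures may look slightly less favourable.
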